#### 7. 4 day blood collection

Participants discharged from the hospital within four days following angiography will be asked

to provide a blood sample 4 ( $\pm$ 1) days following the angiogram. Options for this blood draw may include, but not be limited to: 1) returning to the study VA; 2) having a mobile phlebotomy service draw the blood; or 3) having the blood drawn at a non-study VA site such as a Community-Based Outpatient Clinic (CBOC) or another VA facility closer to the participant’s home.

We chose this time frame to assess post-procedure renal function as almost all patients who develop CIAKI have an elevated SCr within 4 days. One aliquot of this sample will be sent to the central study laboratory to assess the development of CIAKI. A second aliquot from this sample will be delivered to the nearest VA laboratory in order for the practitioner who performed the angiogram to ascertain whether the patient experienced a rise in SCr. This approach will obviate the need for the patient to have more than one blood draw to assess for the development of CIAKI for study and clinical purposes. For patients who remain hospitalized for at least 4 ( $\pm$ 1) days following angiography, a blood sample will be drawn at 4 ( $\pm$ 1) days post-procedure. One aliquot of this sample will be sent to the central study laboratory for subsequent analysis for the development of CIAKI, while a second aliquot will be delivered to the hospital laboratory for the primary provider to review whether the patient experienced a post-procedure rise in SCr.

To ensure patient safety and assist providers, research personnel will notify the provider who performed the angiography that a 4 ( $\pm$ 1) days SCr will be processed in the VA laboratory as part of the study and will send an encrypted email to the patients’ primary provider describing the results of this 4 ( $\pm$ 1) days post-procedure SCr within 2 days of the completion of this test.

Since this creatinine determination is part of the secondary end-point, it is very important that the blood collection be done at 4 ( $\pm$ 1) days after angiography. We recognize that unforeseen circumstances may preclude collection within this window. Under such circumstances the blood should be collected as soon as possible and most proximate to 5 calendar days after the date of angiography. In the event the blood is obtained before 3 or after 5 days following angiography, a protocol deviation should be completed.

8. Day 5 post procedure assessment

(5 days post angiography, allowable range 5-8 days post angiography)

Five days post-angiography, research personnel will review the electronic medical record and perform a structured telephone interview with the patient. For patients who remain hospitalized at this time point, research personnel will speak with them in-person. Beginning on the day of the patient’s angiography, the date and number of NAC/placebo capsules taken will be documented. Reasons for non-compliance will be collected. Research personnel will also review the EMR to verify that NAC/placebo was administered appropriately (at least one hour prior to the procedure and then again at least one hour following the procedure) on the day of the angiography procedure.

During the EMR review and follow-up call (or visit to the patient in the hospital), research personnel will inquire about any adverse events the patient experienced, including any hospitalizations or the need to begin dialysis. To assess the adequacy of patient blinding to the interventions, research personnel will also ask participants to guess which IV fluid arm of the study they were assigned to and whether they received NAC or placebo capsules.

Finally, research personnel will verify that the patient had their 4-day blood sample collected.

We recommend that this contact should be made 5 days after angiography, with an allowable range of 5-8 days post angiography. We recognize that sometimes it may be difficult to contact a patient within this window. However, it is important to collect the required data, which should be done even if done after the recommended time frame has elapsed. It will not be considered a protocol deviation as long as the required data are collected and there is progress note documenting the attempt to schedule the data collection during the recommended time frame.

9. Day 35 post procedure assessment

(35 days post angiography, allowable range 35-49 days post angiography)

Thirty five days following the angiography, research personnel will review the electronic medical record and perform a structured telephone interview with the patient to inquire about any adverse events they experienced related to study participation.

We recommend that this contact should be made at 35 days after angiography, with an allowable range of 35-49 days. We recognize that sometimes it may be difficult to schedule a patient within this window. However, it is important to collect the required data, which should be done even if done after the recommended time frame has elapsed. It will not be considered a protocol deviation as long as the required data are collected and there is progress note documenting the attempt to schedule the data collection during the recommended time frame.

10. Day 90 post procedure assessment

(90 days post angiography, allowable range 90-104 days post angiography)

*a. 90 day blood collection*

In advance of the patient's 90 day assessment, they will be contacted by research personnel regarding their 90 day blood collection. The blood sample obtained will be sent to the Central Laboratory for Scr measurement. Patients who are willing and able will return to the study VA at which their angiogram took place 90 days (allowable range of 90-104 days) following their index angiogram to provide this blood sample. Other options for this blood draw may include, but not be limited to: 1) having a mobile phlebotomy service draw the blood; or 2) having the blood drawn at a non-study VA site such as a Community-Based Outpatient Clinic (CBOC) or another VA facility closer to the participant's home.

If a participant initiates renal replacement therapy (intermittent hemodialysis, peritoneal dialysis, continuous renal replacement therapy [CRRT], or prolonged intermittent renal replacement therapy [PIRRT]) within 90 days of the index procedure, the study coordinator will collect the 90-day blood draw based on the following criteria:

- If the participant initiates renal replacement therapy within 90 days of the index angiography procedure and continues to require renal replacement therapy on or after day 90, the 90-day blood draw will not need to be collected
- If the participant initiates renal replacement therapy within 90 days of the index angiography procedure but recovers kidney function and renal replacement therapy is discontinued prior to day 90, the participant should have his/her 90-day blood drawn

Since this creatinine determination is part of the primary end-point, it is very important that the blood collection be done 90 days after angiography, with a target range of 90-104 days, and with an allowable range of 90-180 days. We recognize that unforeseen circumstances, such as patient hospitalization outside the VA system, may preclude collection within the 90-104 day range. Under such circumstances the blood should be collected as soon as possible and most proximate to 90 days within 180 days and a protocol deviation should be noted if outside the target range of 90-104 days.

This 90-day SCr value will be used to assess for evidence of persistent decline in kidney function. In subjects with a  $\geq 50\%$  increase in SCr between their baseline and 90 day measurements, a confirmatory SCr measurement will be obtained. Options for this blood draw may include, but not be limited to: 1) returning to the study VA; 2) having a mobile phlebotomy service draw the blood; or 3) having the blood drawn at a non-study VA site such as a Community-Based Outpatient Clinic (CBOC) or another VA facility closer to the participant's home. For purposes of determining whether the endpoint of a  $\geq 50\%$  increase in SCr at 90 days (persistent decline in kidney function) has been met, both SCr values will need to be  $\geq 50\%$  higher than baseline and mean of these two SCr will be used. If the 50% increase is confirmed, research personnel will notify the patient's primary care provider using an institutionally approved notification method.

Reimbursement will be provided for travel expenses to have study-related blood draws if these are not done by the mobile specimen collection agency. This payment will be dispersed by the local site according to their procedures. Other than travel reimbursement, patients will not receive any payment for their participation in this study.

*b. 90 day assessment*

Ninety days following the index angiogram, research personnel will review the electronic medical record and perform a structured telephone interview with the patient. The electronic medical record review will specifically focus on assessing the development of any of the following primary and/or secondary end-points within the VA Healthcare System:

- death including date based on medical record documentation
- need for renal replacement therapy including date of initiation and duration of therapy
- hospitalization including date and primary and secondary hospital discharge diagnoses (to assess for ACS, HF, and/or CVA)

The 90-day structured telephone interview with the patient will complement the electronic medical record review. This telephone interview will verify data that was abstracted from the electronic medical record and enable research personnel to inquire about hospitalizations at non-VA facilities that would not have been captured in the VA electronic medical record. For any patients who were hospitalized outside the VA, the research personnel will obtain the requisite release of information form(s) from the patient. Once the completed form(s) is received, research personnel will acquire the pertinent medical records to assess for the development of any of these outcomes. In addition, death within this 90-day time period will be ascertained by linking our study database with the VA Beneficiary Identification and Records Locator System, National Center for Health Statistics National Death Index database, Social Security Administration's Death Master File, and/or other similar databases.

We recommend that the telephone contact be performed 90 days after the initial angiography, with an allowable range of 90-104 days. We recognize that sometimes it may be difficult to schedule a patient within this window. However, it is important to collect the required data, which should be done even if done after the recommended time frame has elapsed. It will not be considered a protocol deviation as long as the required data are collected and there is progress note documenting the attempt to schedule the data collection during the recommended time frame.

11. 1-year assessment

We will link our database with the United States Renal Data System to ascertain the development of ESRD and the date of initiation of renal replacement therapy within one year of the index angiographic procedure. Finally, death within this 1-year period will be ascertained by linking our database with the VA Beneficiary Identification and Records Locator System, National Center for Health Statistics National Death Index database, Social Security Administration’s Death Master File and/or other similar databases. Timing the performance of these linkages will depend upon the availability of data from the USRDS and the vital status registries, which may lag by 12-18 months after the end of each calendar year.

## VIII. POTENTIAL PITFALLS OF THE PROPOSED STUDY DESIGN AND ALTERNATIVE STUDY DESIGN CONSIDERATIONS

### A. Study Hypotheses

#### 1. Relationship between CIAKI and patient-centered outcomes

Our study design is based on a conceptual model in which CIAKI is not only associated with, but is the proximate event in a direct causal pathway leading to serious, adverse downstream outcomes. While we postulate that CIAKI mediates serious, adverse downstream events, we recognize that it is possible that the small changes in kidney function that define CIAKI may simply represent a marker of underlying cardiac and/or vascular disease and reflect pre-procedure risk for morbidity and mortality. Thus, it is possible that the proposed interventions may reduce the incidence of CIAKI, defined by change in SCr, but not affect the incidence of serious, adverse, patient-centered outcomes. While this outcome might be viewed as disappointing, we believe that such a finding would be extremely significant and would have a substantial impact on clinical care and resource allocation.

Similarly, we recognize that post-angiography AKI has etiologies other than iodinated contrast, most notably hypotension and atheroembolic disease. Our interventions are unlikely to impact the development of AKI in such cases. To address this possibility, we will conduct sensitivity analyses in which we will evaluate the development of CIAKI using the same threshold change in SCr, but exclude patients who experienced hypotension, underwent cardiac or non-cardiac vascular surgery within the 4 days following angiography, and/or had a documented cause for acute kidney injury in the primary or secondary discharge diagnoses, other than contrast associated AKI.

#### 2. Effectiveness of Bicarbonate and NAC

Our hypotheses that bicarbonate (compared to saline) and NAC (compared to placebo) will decrease the incidence of serious, adverse 90-day outcomes are based on the purported effectiveness of these interventions in preventing the short-term changes in SCr that define CIAKI. We recognize that if bicarbonate (compared to saline) and NAC (compared to placebo) are not effective for the prevention of CIAKI, we are unlikely to observe an effect of these

interventions on the events that comprise our primary study endpoint. For this reason, we have included prevention of CIAKI as a key secondary outcome.

## **B. Study Population**

### **1. Inclusion of patient undergoing coronary or non-coronary angiography**

Most past studies of CIAKI have focused on patients undergoing coronary angiography. We propose enrolling patients undergoing either coronary or non-coronary angiography. While including patients undergoing non-coronary angiography will increase the heterogeneity of the study population, data from our prospective cohort study suggest that CIAKI and serious adverse events are even more common following non-coronary angiography than coronary angiography. Moreover, non-coronary angiograms make up approximately one-third of angiographic procedures performed within the VA. Therefore, we believe that despite the effect on patient heterogeneity, inclusion of patients undergoing non-coronary angiography will enrich the study population with high-risk patients, significantly increase the number of patients available for recruitment, and broaden the generalizability of the study findings.

### **2. Exclusion of patients undergoing contrast-enhanced computed tomography**

There are past trials of interventions for the prevention of CIAKI that included and/or were focused exclusively on patients undergoing contrast-enhanced computed tomography. Although inclusion of patients undergoing contrast-enhanced computed tomography in our proposed trial would substantially increase the pool of eligible patients, our prior observational cohort study of Veterans undergoing contrast-enhanced procedures found that CIAKI was less common following computed tomography than after angiography. Inclusion of these lower risk patients would decrease the anticipated event rate and result in the need for a considerably larger study than we have proposed. Nevertheless, interventions to decrease the risk of CIAKI and serious, adverse, patient-centered outcomes following angiographic procedures will likely be applicable to high-risk patients undergoing contrast-enhanced computed tomography.

### **3. Criteria for selection of high-risk patients**

Our study targets patients who are at high risk for CIAKI and serious, adverse events following angiography. While the inclusion of lower risk patients would broaden the study population, it

would result in the need to recruit a considerably larger number of participants and would likely add complexity to and decrease the feasibility of the study. We chose to define our patient population as being at high-risk based on the presence of underlying chronic kidney disease, with diabetes serving as an amplifier of risk in the setting of impaired renal function. We chose this approach because chronic kidney disease is commonly cited as the primary risk factor for CIAKI, is easily assessed, and is present in a large proportion of patients undergoing angiographic procedures. We recognize that other clinical conditions (e.g., heart failure, intravascular volume depletion) are also associated with an increased risk for CIAKI and adverse, downstream outcomes and could be used to define a study population as high-risk. However, assessment of the presence and severity of heart failure and intravascular volume depletion is somewhat subjective and therefore more difficult to protocolize.

### **C. Study interventions**

#### **1. Fluid administration**

There is no consensus among experts on the optimal rate and duration of IV fluid administration for the prevention of CIAKI or single protocol for the administration of IV fluid that has been shown to be the most effective. Individual patient circumstances and provider preferences commonly dictate the volume and duration of IV fluids administered. We anticipate that some providers might be unwilling to have their patients participate in this trial if they have no control over the rate or duration of IV fluid administration in their patients. For these reasons, rather than adopting one of the multitude of fluid administration protocols employed in prior clinical trials for the prevention of CIAKI, the planning committee decided that a more flexible approach that specified a minimum volume and duration of administration of IV fluids would be more acceptable to providers without deviating from what would be considered appropriate preventive care. While we believe that this approach will provide a volume of IV fluid that is comparable to that used in most recent trials comparing bicarbonate and saline, it is possible that this strategy could result in systematic differences in the rate and duration of fluid administration in patients randomized to bicarbonate and saline. While this is very unlikely given the large trial size and blinding of fluid composition, we will closely monitor duration and volumes of fluid administration across groups.

## 2. Complications of fluid administration

We anticipate that some patients will develop volume overload/pulmonary edema and/or elevated left ventricular end-diastolic pressure during angiography. In such instances, providers performing angiography may discontinue post-procedure IV fluids resulting in patients failing to receive study IV fluid following the angiogram. It is likely that this event will occur in a small proportion of patients and be equally distributed across treatment arms. While the volume of study IV fluid administered pre, during and post-procedure will be carefully recorded for all patients, given the importance of patient safety, we believe it would be inappropriate to require the administration of post-procedure study IV fluid in such instances. Since all analyses will be based on the intent-to-treat principle, these patients will not be excluded from the study analyses.

## 3. Route and dose of NAC administration

There is currently no universally accepted protocol for the route of administration of NAC for the prevention of CIAKI. While most prior studies used oral NAC, a small number of studies administered NAC intravenously. The primary putative advantage of IV administration is a reduction in first-pass inactivation of NAC by the liver after enteric absorption, thereby increasing delivery to the kidneys. Notwithstanding this theoretical benefit of IV NAC, we selected the oral route of administration for three reasons. First, there are inadequate clinical data to demonstrate that the theoretical benefits of IV NAC translate into greater clinical effectiveness than oral NAC. Second, IV administration of NAC is associated with a considerably higher risk for adverse reactions, including anaphylaxis, than the oral formulation. Finally, the IV preparation of NAC is considerably more expensive than the oral preparation.

Although the optimal dose of NAC for the prevention of CIAKI has not been clearly established, we have chosen to administer 1200 mg twice daily for four reasons. First, clinical trials that assessed the impact of dose on the incidence of CIAKI and serious, adverse outcomes demonstrated a benefit to higher dose NAC. Second, data from experimental models suggests a dose-dependent effect of NAC with higher doses associated with less renal tubular damage. Third, there is little safety risk with higher doses of NAC compared to lower doses of

NAC. Finally, current opinion-based recommendations for the prevention of CIAKI advocate the use of 1200 mg of NAC twice daily.

#### 4. Duration of study interventions

The optimal duration of strategies for prevention of CIAKI is not known. As discussed in section VII.D.2, there are preliminary data indicating that iodinated contrast may persist in the kidney for several days following contrast-enhanced procedures. While it is not known whether this persistent contrast contributes to, or is a marker of renal injury, the planning committee felt that extending the administration of oral NAC to 5 days could be beneficial with little to no safety risk. Unlike the safety of longer duration NAC, extending the duration of IV fluids poses a risk for volume overload/pulmonary edema, would require prolonged hospitalization, and could be viewed unfavorably by both patients and providers. There was consideration given to providing oral sodium bicarbonate and oral sodium chloride tablets for 5 days. However, to match the amount of bicarbonate or saline given intravenously, nearly 7 grams of oral sodium bicarbonate and 5 grams of oral sodium chloride would have to be given daily, which would pose safety concerns regarding exacerbation of heart failure and/or worsening of hypertension. While lower doses of oral sodium bicarbonate and sodium chloride could be used, there are no preliminary clinical data to support this approach for the prevention of CIAKI or serious, adverse downstream outcomes. Therefore, although we extended the use of NAC to 5 days, our bicarbonate/saline intervention will be limited to IV fluid administration in the immediate peri-procedural period.

#### 5. Potential for interaction between bicarbonate and NAC

Implicit in our use of a 2 x 2 factorial design is the *a priori* assumption that there is minimal to no interaction between the two study interventions. That is to say, the relative effect of bicarbonate in patients receiving NAC is the same as in patients receiving placebo, and the benefit of NAC is the same in patients receiving bicarbonate or saline. We acknowledge, however, that there are only limited data evaluating this interaction, and that these data are restricted to the prevention of CIAKI rather than prevention of serious, adverse outcomes. For example, in a recent systematic review and meta-analysis of IV sodium bicarbonate for the prevention of CIAKI, Zoungas et al. observed no difference in the incidence of CIAKI following

sodium bicarbonate administration with or without concomitant administration of NAC (p for heterogeneity = 0.73) in four studies which included data on 983 patients. Similarly, Brown and colleagues found that combination treatment of NAC with IV sodium bicarbonate reduced CIAKI by 35% compared to NAC with saline in a meta-analysis of 10 randomized controlled trials. In an experimental model, Romano et al. found no interaction between bicarbonate and NAC in the prevention of renal tubular cell apoptosis following exposure to iodinated contrast media. Nonetheless, these data are insufficient to definitively exclude the possibility of an attenuation of benefit associated with combined therapy. We have taken this into consideration in our statistical analysis (*vide infra*); as designed, the study will retain greater than 80% statistical power even in the presence of a 50% attenuation in effect with combined therapy.

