**Table 10 - Sample size for selected response rates**

| Rate in control (C) group | Rate in treatment (T) group | % reduction (C -T)/C | Total sample size 80% power b | Total sample size 90% power b |
|---------------------------|-----------------------------|----------------------|--|--|
| 7.0                       | 4.90                        | 30%                  | 5,030                                    | 6,562                                    |
| 7.0                       | 5.25                        | 25%                  | 7,432                                    | 9,688                                    |
| 7.0                       | 5.6                         | 20%                  | 11,924                                   | 15,546                                   |
| 8.7                       | 6.1                         | 30%                  | 3,995                                    | 5,196                                    |
| 8.7 a          | 6.52 a           | 25% a     | 5,900 a                       | 7,680 a                       |
| 8.7                       | 7.0                         | 20%                  | 9,440                                    | 12,317                                   |
| 10.4                      | 7.3                         | 30%                  | 3,271                                    | 4,285                                    |
| 10.4                      | 7.8                         | 25%                  | 4,844                                    | 6,314                                    |
| 10.4                      | 8.3                         | 20%                  | 7,763                                    | 10,123                                   |

a rates and sample size for proposed model (with adjustment for losses to follow-up)

b adjusted for an O'Brien-Fleming stopping rule with one interim and one final test of hypothesis and considering a two-sided type I error = 0.025.

Thus, based on a 90 day event rate of 8.70% in the control group (i.e., saline or placebo) and

[name], [name]: CSP#578 “Prevention of Serious Adverse Events Following Angiography”  

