**Table 11 - Impact of Interaction between Bicarbonate and NAC on Statistical Power**

| % attenuation from interaction between Bicarbonate & NAC | Rate in subjects assigned to Bicarbonate/NAC | Rate in treatment (T) group | Rate in control (C) group | % reduction (C-T)/C | Power |
|--|--|-----------------------------|---------------------------|---------------------|-------|
| No interaction   | 5.60 %                                       | 6.52%                       | 8.7%                      | 25%                 | 90%   |
| 10% attenuation  | 5.78%  | 6.62%                       | 8.7%                      | 23.9%               | 87.5% |
| 20% attenuation  | 5.97%  | 6.71%                       | 8.7%                      | 22.9%               | 84%   |
| 30% attenuation  | 6.15%  | 6.81%                       | 8.7%                      | 21.7%               | 79.3% |
| 50% attenuation  | 6.53%  | 6.99%                       | 8.7%                      | 19.7%               | 69.4% |

Thus, the study will retain nearly 80% statistical power with the proposed sample size of 7,680 patients even if an interaction between bicarbonate and NAC leads to a 30% attenuation of their combined effect.

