A total of 7680 subjects recruited from the 33 Veterans Health Administration (VHA) centers are expected to be randomized equally to each of the 4 groups as shown in Table 1 below. An additional 1000 subjects are expected to be enrolled in the 12 non-VHA sites in Australia to augment the data collected in the US.

Table 1. Intervention Groups

	Bicarb	Saline
NAC	Group1: NAC+Bicarb	Group2: NAC+Saline
Placebo	Group3:Placebo+Bicarb	Group4:Placebo+Saline

Compare
NAC vs. Placebo
(Groups 1+2 vs. 3+4)

Compare Bicarb vs. Saline
(Groups 1+3 vs. 2+4)

The primary objective:

As the primary objective, the trial will test two hypotheses:

- (#1) IV isotonic bicarbonate is more effective than saline, and
- (#2) NAC is more effective than placebo

in prevention of major adverse kidney events (need for acute dialysis or 50% increase in serum creatinine at 90 days after angiography) and death (MAKE-D) following coronary and non-coronary angiography. This will be accomplished by comparing the incidence of MAKE-D in groups 1 and 3 combined to groups 2 and 4 combined for hypothesis (#1), and by comparing groups 1 and 2 combined to groups 3 and 4 combined for hypothesis (#2). See **3.5.1**.

Secondary Objective:

The trial will also evaluate the effectiveness of the study interventions for the prevention of 5 individual secondary endpoints (section **3.5.2**) by comparing the treatment groups as in the primary objective. The secondary endpoints are:

- 1)contrast induced acute kidney injury (CIAKI) at day5 after angiography
- 2)death
- 3)major adverse kidney endpoints (MAKE)
- 4)hospitalization with acute coronary syndrome, heart failure, or cerebrovascular accident
- 5)all-cause hospitalization.

Tertiary Objective:

The trial will explore the effectiveness of the study interventions for the prevention of the following outcomes (see **3.5.3**), within one year following coronary or non-coronary angiography by comparing the treatment groups as in the primary objective. The tertiary endpoints are:

- 1) development of end stage renal disease (ESRD), and
- 2) death.

3. Investigational Plan

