These estimations assume no interaction between the two active interventions, are adjusted for an O'Brien-Fleming stopping rule with one interim and one final test of hypothesis, and allow for an overall two-sided type I error of 2.5% for each hypothesis being tested. Hence, each of the interim hypothesis for main effect will be tested at p=0.001 level (allowing for 0.1% Type I error), and each of the final hypothesis for main effect will be tested at p=0.024 level (allowing for 2.4% Type I error).

If an attenuation of effect is present due to interaction between Sodium Bicarbonate and NAC, adjustment to the statistical power for 10% to 50% attenuation are given as follows.

Table 5. Statistical Power in the Presence of Effect Attenuation.

% attenuation from interaction between Bicarbonate & NAC	Rate in Bicarbonate/NAC	Rate in treatment (T) group	Rate in control (C) group	% reduction (C-T)/C	Power
No interaction	5.60 %	6.52%	8.7%	25%	90%
10% attenuation	5.78%	6.62%	8.7%	23.9%	87.5%
20% attenuation	5.97%	6.71%	8.7%	22.9%	84%

30% attenuation	6.15%	6.81%	8.7%	21.7%	79.3%
50% attenuation	6.53%	6.99%	8.7%	19.7%	69.4%

Sample recruitment and subsequent event rates will be summarized and presented to the DMC bi-annually as outlined in section 7 below. These reports will be used for monitoring the progress of the study and any modification to the recruitment schedule or the statistical analysis plan will be at the recommendation of the DMC.

5. Statistical Methods

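### Protocol VIII.C.5 claims more than 80% power at 50% attenuation under combined therapy; Protocol Table 11 and SAP Table 5 give 69.4%

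*Protocol*

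**What the plan says.** Protocol VIII.C.5 explains that the 2 x 2 factorial design assumes little or no interaction. It concedes that the data on this are limited and confined to CIAKI, and that they cannot exclude some loss of benefit when both treatments are given. It then says this was allowed for in the statistical analysis, to be found later in the document, and that, as designed, "the study will retain greater than 80% statistical power even in the presence of a 50% attenuation in effect with combined therapy".

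The later text is in Protocol XVII.F. Table 11 lists power by degree of attenuation: 90% with none, 87.5% at 10%, 84% at 20%, 79.3% at 30% and 69.4% at 50%. The sentence under the table makes a weaker claim, and makes it for 30% attenuation, not 50%: "the study will retain nearly 80% statistical power with the proposed sample size of 7,680 patients even if an interaction between bicarbonate and NAC". The text before the table puts power at 40% for complete attenuation.

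SAP section 4 introduces its Table 5 with the words "adjustment to the statistical power for 10% to 50% attenuation are given as follows" and prints the same five rows, including 69.4% at 50%.

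**The concern.** Two current parts of the protocol give different power for the same scenario, and the SAP sides with the less favourable one. The sentence in VIII.C.5 is the only quantitative reassurance that section offers after admitting that attenuation cannot be ruled out. A reader who stops there would take the risk of missing a real main effect at 50% attenuation to be under 20%. On the tabled figure it is 100% − 69.4% = 30.6%. That bears on how a null main effect would be read and on how robust the design is thought to be to its central assumption.

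**Working it through.** **Inputs (Protocol XVII.A.2 and XVII.F)**
- Total N 7,680, equal allocation, 3% loss: 7,680 × 0.97 ≈ 7,450 evaluable, or 3,725 on each side of a main-effect comparison.
- Two-sided alpha 0.025 per hypothesis, so z = 2.2414.
- Model 2 cell rates: 5.59% (both treatments), 7.46% (either alone), 9.95% (neither).

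**Step 1. What 50% attenuation means.** The combined cell loses half of its added benefit:
- Combined cell: 5.59 + 0.5 × (7.46 − 5.59) = 6.525%, printed as 6.53%.
- Treatment margin: (6.525 + 7.46)/2 = 6.99%.
- Control margin: (7.46 + 9.95)/2 = 8.705%, printed as 8.7%.

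These are Table 11's entries. They also match the wording of VIII.C.5, which speaks of attenuation with combined therapy, so both places describe the same scenario.

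**Step 2. Formula.** Pooled two-proportion test, n per side, p̄ the mean of the two rates:

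power = Φ{ [ |p₁ − p₂| − z·√(2p̄(1 − p̄)/n) ] / √([p₁(1 − p₁) + p₂(1 − p₂)]/n) }

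**Step 3. The 50% row.** With p₁ = 0.087, p₂ = 0.0699 and n = 3,725, the standard errors are 0.006230 (null) and 0.006227 (alternative):

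(0.0171 − 2.2414 × 0.006230)/0.006227 = 0.5035, and Φ(0.5035) = 69.3%.

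With the unrounded margins (8.705% and 6.9925%) the result is 69.4%.

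**Step 4. The whole series**

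| Attenuation | Treatment v control | Recomputed | Documents |
|---|---|---|---|
| None | 6.52% v 8.7% | 90.5% | 90% |
| 10% | 6.62% v 8.7% | 87.2% | 87.5% |
| 20% | 6.71% v 8.7% | 83.6% | 84% |
| 30% | 6.81% v 8.7% | 79.1% | 79.3% |
| 50% | 6.99% v 8.7% | 69.3% | 69.4% |
| Complete | 7.45% v 8.7% | 39.7% | 40% |

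Power passes below 80% between 28% attenuation (80.2%) and 30% (79.3%, from the unrounded treatment margin).

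**Step 5. Could another reading reach 80% at 50% attenuation?**

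| Reading | Power |
|---|---|
| No losses (3,840 per side) | 70.7% |
| Final critical value z = 2.25, 3% loss | 69.0% |
| Two-sided alpha 0.05, 3% loss | 78.4% |
| Two-sided alpha 0.05, no loss | 79.6% |
| N = 8,680 (non-VA patients added), 3% loss | 75.1% |
| N = 8,680, no loss | 76.5% |
| N = 8,680 and alpha 0.05 together | 83.1% to 84.2% |

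Only the last exceeds 80%. It drops the 2.5% alpha per hypothesis and adds patients whom SAP section 2 counts separately from the 7,680, so it is not the study as designed.

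**Step 6. N needed for 80% power.** At 6.99% v 8.7% the same formula needs 9,398 evaluable patients, or 9,398/0.97 ≈ 9,689 enrolled. That is 9,689 − 7,680 = 2,009 more than planned.

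**The case against.** The strongest objection is about weight. The sentence stands in a narrative section on pitfalls and sends the reader to the correct table. The statistical section gives 69.4% at 50% and 40% at complete attenuation, and draws its own conclusion only at 30%. The SAP repeats the table. The design's limited robustness to interaction is therefore disclosed in both documents. This stands: the defect is one sentence, and the trial is not shown to be under-powered for the scenario it was sized on.

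A second objection concerns Table 10 as support. Its row for 8.7% v 7.0% lists 9,440 patients for 80% power, which looks like confirmation of Table 11. But that row is labelled a 20% reduction, and 8.7% × 0.80 = 6.96%, printed as 7.0. At 6.96% the evaluable N is 9,060, and 9,440/9,060 = 1.042, about the 4% to 5% by which the other rows exceed their evaluable N (for example 4,844/4,650 = 1.042). So 9,440 is an inflated figure for a slightly larger effect, and it understates the shortfall at 6.99%. This also stands. Table 10 points the same way, but the conclusion should rest on Table 11 and SAP Table 5.

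The 8,680 scenario is likewise unnecessary to the point, since the sentence speaks of the study as designed. It is shown only because it is the most obvious possible rescue, and it fails.

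**Conclusion.** The point holds. At 50% attenuation the planned design has about 69% power, not more than 80%. The overstatement is more than 10 percentage points, and the type II error is about 31%. The tables reproduce from their own inputs, so the error lies in the last sentence of VIII.C.5.

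This rests on the protocol's Model 2 rates, its definition of attenuation, 3% loss, two-sided alpha 0.025, and a fixed-sample normal approximation for the main-effect comparison. Using the planned final critical value moves the result by only 0.3 points. The consequence is limited to the statement itself.

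**What to change.** Replace the last sentence of Protocol VIII.C.5 with one that matches Table 11, for example: with 7,680 patients, power is nearly 80% (79.3%) at 30% attenuation of the combined effect and falls to about 69% (69.4%) at 50% attenuation (Table 11).

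The cost is one sentence and a less favourable stated power. The sample size, Tables 10 and 11, SAP Table 5, the stopping boundary and the analyses stay as they are.
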